The current 3D intraoral scanners capture the color of the oral tissues by emitting visible white light. A recently developed 3D intraoral scanner manufactured and CE marked by 3Shape A/S. Denmark, is also able to emit visible blue light (405 nm wavelength) (17) that allows capturing fluorescence from the oral tissues. Fluorescence is one of the most promising technologies for accurate detection of the early stages of enamel demineralization (18, 19, 20), but is currently available only in 1D or 2D devices. The main limitation of the existing devices featuring fluorescence, as already mentioned, is the challenge in comparing single images obtained at different points in time, which is at large influenced by imaging artifacts and noise. Imprecision in the comparison of these images compromises the ability to accurately monitor progressive demineralization of the dental hard tissues. To the best of our knowledge, there is no intraoral scanner reported in the scientific literature that combines fluorescence with 3D imaging. Thus, we hypothesize that this new intraoral scanner will benefit the monitoring of dental hard tissues and will aid dentists to identify early changes in tissue mineralization. With this method it is only possible to examine the tooth surfaces that are visible and directly exposed into the mouth (i.e. the smooth free surfaces and the occlusal fissures); the areas between the teeth (i.e. the approximal surfaces) cannot be visualized and therefore cannot be examined using the scanner.

3. Methods

Study execution

The participants will be monitored for a period of 1 year. The study will last approximately 2 years in total, with the baseline examination taking place in the beginning of 2019 and the last examination in the Spring – Winter 2020. Detailed plan of the study is shown in Table 1.

Information about the project

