A second appointment will be scheduled to conduct the oral health examination, including intraoral scanning and 2 bitewing radiographs (BW). The responsible researcher will request the participants to provide any recently available BW, in case these are not older than 6 months. No study-related examination will be conducted before the signed parental consent form has been obtained by the responsible researcher. The participants will not be offered any treatment other than routine professional tooth cleaning, which is important for a thorough visual examination and scanning of the teeth. In case any oral disease is detected, the participants will be referred to their dentist for treatment.

If no radiographs are available from the past six months, BW of the upper and lower posterior teeth on both sides will be taken. Since radiographs are part of the participants' annual dental check-up, these will be made available to the participants' dentist. Additionally, an oral examination will be conducted, and the condition of teeth, gums and fillings will be registered. The approximal plaque accumulation will be registered by employing the approximal plaque index (21). Thereafter, the teeth will be professionally cleaned, and the presence of caries lesions will be registered based on the visual and radiographic assessments. Caries lesions will be characterized as active or inactive and classified according to the ICDAS criteria into 7 stages (22). Furthermore, the presence of other visible defects on the oral hard tissues (*i.e.* erosive – abrasive lesions) will be registered using appropriate criteria (*i.e.* BEWE index for erosive tooth wear) (2, 23).

Subsequently, both the upper and lower jaw of the participant will be scanned using the intraoral scanner (Trios 4, 3Shape Trios A/S, Denmark). Scans will be obtained using visible white and blue light (wavelength 415 nm).

At the end of the session, the participants will be classified into different risk groups (low, moderate, high) according to the clinical findings and the information collected from the diet

history and the oral hygiene habits questionnaire (Appendix 1, 2). According to this classification, the responsible researcher will set the follow-up intervals for each participant (3-12 months). All patients will be monitored for 1 year.

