The same clinical procedures will be followed on the follow-up examinations (3 or 6 months) as well as on the final examination (1-year follow-up). The diet history, the oral hygiene habits questionnaire and the BW radiographs will be repeated only on the final examination (Table. 1).

4. Statistics

Paired T-test will be conducted to identify differences between the clinical scores at the baseline and the subsequent follow-ups for the different conditions investigated (*i.e.* caries score, erosion score) (24).

Exploratory analysis of the data extracted from the 3D scans will be conducted and compared to the clinical scores. Pearson correlation coefficients between the clinical scores and scores obtained from the 3D scans will be calculated. Paired t-test will be conducted to compare the number of lesions per patient (*i.e.* caries, tooth wear) that will be detected with the 2 different methods (scanning and clinical-radiographic examination).

All statistical analysis will be conducted using a 95% level of confidence.

Information regarding the sample size calculation using power analysis is provided on the following paragraph (§5. Research subjects - Sample size calculation)

5. Research subjects

The participants in this research project will be adolescents (12-16 years old) and young adults (18-19 years old) in Denmark and in Greece respectively.

As previously mentioned, this project will assess the ability of the intraoral scanner combining fluorescence to detect and monitor initial changes in the dental hard tissues, with special focus on caries: the most prevalent oral disease. The most important benefit expected by using the fluorescence method is the detection of initial lesions on dental surfaces directly exposed to the mouth. Fissure lesions in permanent posterior teeth usually appear in the long-lasting period of tooth eruption, *i.e.* from when the tooth first appears in the mouth until it contacts with the opposite dentition (28). Eruption of the first permanent molar starts around the ages of 6-8 years, the second molar at 12-14 years (28) and the third molar at 17-18 years. During the eruption period, the posterior teeth are at a higher risk for developing fissure caries. For the second permanent molars, this period can last up to 27 months form the first appearance in the mouth (~12 years old) (29) though for the third molars this period is usually longer.

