The initial state of the caries lesion is short-lived before progression of the disease. In older patients, caries lesions in fissures are either found at more advanced stages or they have already been treated by the dentist (*i.e.* sealed, filled or extracted as in the case of third molars) (28). Although initial caries lesions can be found in older patients, such initial lesions are located on the surfaces between the teeth, which are not visible to the intraoral scanner and therefore cannot be detected using this method.

For these reasons, the age group is set from 12 to 19 years. It is necessary to conduct the study on this group of young people, as the study is expected to benefit them directly. The same benefits are not expected if the study is conducted in older adults.

The early diagnosis of initial lesions in the young participants is more beneficial as it will allow the implementation of preventive measures to stop the progression of the disease. This will decrease the complexity of the treatments needed in the target group, as the initial lesions can be treated with minimal or non-invasive approaches. Thus, the economic burden for the state regarding treatment expenses of the adolescents and the individual costs related to future dental treatment will be reduced.

Inclusion criteria:

- Young people (12-19 years old) without chronic diseases.

Exclusion criteria:

- Participants in need of complex dental treatment (*e.g.* extensive restorative work, extractions, prosthetic treatment).
- Participants using partial/complete removable dentures or other appliances (*i.e.* orthodontic devices).

Sample size calculation

Caries data was used in order to calculate the desirable sample size for the current study, as that is the most prevalent oral disease in young patients and is widely investigated in epidemiological studies (1). Therefore, data regarding initial caries lesions was used for the sample size calculation, assuming that the new method will aid dentists to detect significantly more initial caries lesions compared to traditional methods.

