For the sample size calculation, data collected by the Central Odontology Register of the Danish National Board of Health (Sundhedsstyrelsens Centrale Odontologiske Register SCOR) during the year 2017 from municipal dental clinics at 98 different municipalities in Denmark was used. According to the data, an average of 3.08 initial lesions, with a standard deviation of 1.23 were identified on 15-year old patients at the different municipalities. In this study, the desirable power was set on 90%, the level of significance on 5% and the effect size on 30% (1 lesion). By applying these parameters, the sample size was calculated to be 64 adolescents. Nevertheless, as a 10% drop-out is expected for this type of study, the final number of participants to be included in the study should be 70.

6. Risks, side effects and shortcomings in short and long term

Risks

This study will be conducted on healthy persons, on whom the procedures followed in this study are assumed to have a negligible risk.

No risk is related to the clinical visual examination.

Regarding the 3D intraoral scanning procedure, if the scan quality is poor and thus the scan is not useful for the research objectives, the scanning procedure should be repeated. This is of no risk for the patient but represents the inconvenience of a delay of the dental visit.

For the scanning using blue light (wavelength 415nm) possible risks exist. For the participant, light irritation of the mucosa and lips may result from a local, acute overexposure to the strong blue light. This irritation, though, is mild and temporary. For the operator, possible harm to the eyes, especially on the lenses and the retinal tissues, may be caused by long-term cumulative exposure to blue light. These risks are not particular for this specific intraoral device but are

common to any dental equipment that uses blue light. Having these risks in mind, the equipment will be used properly and with care: the exposure time will be limited to 15 seconds per tooth and direct exposure to mucous membranes will be avoided. The equipment will be started only after it has been inserted into the patient's mouth. The operator will avoid looking directly into the mouth and instead will look on the computer screen during the scanning procedure. Eye-protection goggles filtering light under 500 nm are suggested to be used by the operator.

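### The between-method caries count has no tooth-surface limit, so a null result could mean no scanner gain on exposed surfaces or a gain offset by approximal lesions it cannot see

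*Combined protocol and SAP*

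**What the plan says.** Section 4 (Statistics) compares the number of lesions per patient "detected with the 2 different methods (scanning and clinical-radiographic examination") by a paired t-test. It names caries and tooth wear as the lesions and sets no limit by tooth surface.

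The two methods do not see the same surfaces. Section 2b (Background) says of the scanner that "the areas between the teeth (i.e. the approximal surfaces) cannot be visualized and therefore cannot be examined using the scanner". For the comparator, section 3 (Clinical and radiographic examination) says that "the presence of caries lesions will be registered based on the visual and radiographic assessments", the radiographs being bitewings of the posterior teeth on both sides. After baseline, "the BW radiographs will be repeated only on the final examination".

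Section 5 (Research subjects) gives the most important expected benefit as "detection of initial lesions on dental surfaces directly exposed to the mouth". It returns to the field of view when it justifies the age range, saying of older patients that "such initial lesions are located on the surfaces between the teeth, which are not visible to the intraoral scanner and therefore cannot be detected". The sample size calculation rests on "assuming that the new method will aid dentists to detect significantly more initial caries lesions compared to traditional methods", and its data are "an average of 3.08 initial lesions, with a standard deviation of 1.23 were identified on 15-year old patients at the different municipalities". It does not say which surfaces the 3.08 covers. Neither section 4, section 5 nor Table 1 aligns the two counts by surface.

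**The concern.** One count is asked to serve two questions. The first is whether the scanner finds more caries on the surfaces it can see, which is the benefit section 5 puts first. The second is whether it does better than the visual-radiographic examination over the whole mouth, which is how hypothesis 2 in section 2a can be read and what the remark in section 11 about less need for ionizing radiation depends on.

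For the first question, approximal lesions enter one side of the comparison only and pull the difference down, whatever the scanner does on exposed surfaces. For the second, they belong in the count. Section 4 does not say which question its test answers, so a small or null difference would be ambiguous, and a difference in favour of the comparator could reflect field of view alone. The point concerns caries, not tooth wear.

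**Working it through.** **The plan's own figure.** Section 5 gives SD 1.23, an effect of 1 lesion, 90% power and 5% significance. The two-sided formula for two independent means gives n per group = 2 × (1.960 + 1.282)² × 1.23² / 1² = 2 × 10.51 × 1.513 = 31.8, so 32 per group and 64 in total, as stated. (The match is with two independent groups while the planned test is paired. That is a separate matter and is not used here.) The effect was set on the undivided count; the plan defines no visible-surface gain.

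**Direction of the shift.** This needs no figures. Let g be the scanner's mean gain over the comparator on surfaces both can examine, and A the mean number of approximal lesions the comparator registers per patient. The scanner registers none of these, so

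scanner minus comparator = g - A.

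Any A above zero lowers the difference. A result near zero fits g = 0 with A = 0, and equally g = A with both above zero. The total count cannot tell these apart.

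**Visits.** Bitewings contribute to A only at baseline and the final examination. At the 3- or 6-month visits, A could come only from approximal lesions registered visually.

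**Illustration of size.** The documents do not give A. Three assumptions are needed: the 3.08 lesions include a share a that is approximal; the study comparator finds the same mean as the register; and g is 1 lesion. Then A = 3.08a and the net difference is 1 - 3.08a:

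| a | A = 3.08a | Net difference if g = 1 | Net difference if g = 0 |
|---|---|---|---|
| 0% | 0 | +1.00 | 0 |
| 10% | 0.31 | +0.69 | -0.31 |
| 20% | 0.62 | +0.38 | -0.62 |
| 30% | 0.92 | +0.08 | -0.92 |
| 32.5% | 1.00 | 0 | -1.00 |

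The break-even point is a = 1/3.08 = 32.5%. It does not depend on any SD.

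**Why no power figure is relied on.** Power of the paired test depends on the SD of the within-patient differences, which the documents do not give. If each method had SD 1.23 and the between-method correlation were r, that SD would be 1.23 × √(2(1 - r)): 1.739, 1.230 and 0.778 at r = 0, 0.5 and 0.8. With 64 pairs, a two-sided 5% test and g = 1, power would be 88%, 99% and above 99% at a = 10%, and 41%, 69% and 97% at a = 20%. The spread at a = 20% comes from r alone. Moreover, 1.23 is reported across municipalities and may not be a patient-level SD.

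**The case against.** Four arguments on the other side carry weight.

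- **The whole-mouth count is a legitimate comparison.** Hypothesis 2 names visual-radiographic methods as the comparator, and the sample size assumption is set against traditional methods. On that question, lesions the scanner cannot see are a genuine shortfall. This stands. A reader might infer that the planned test is biased or invalid. It is not; it answers a different question from the one section 5 puts first, and the plan does not say which is meant.
- **The effect may be small.** The age range was chosen partly because of the field of view, and section 5 places initial approximal lesions in older patients. Section 2b adds that radiographs are insensitive to early enamel demineralization. This also stands as to size. It does not remove the gap: the plan does not say that 12-19-year-olds have no approximal lesions, it takes bitewings in them, and section 4 counts caries without limiting it to initial stages.
- **The analysis is partly exploratory.** The test follows a sentence on exploratory analysis, and no primary endpoint is named. This softens the point, but the sample size rests on this kind of comparison.
- **Surface-level records may exist.** The documents do not say. If they do, the remedy is cheaper, but a surface-limited analysis would still have to be stated.

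**Conclusion.** The gap is certain from the text; its size is not known. As written, section 4 compares a count that includes approximal caries with one that cannot, and no section aligns them. For detection on exposed surfaces, the difference is shifted against the scanner by the mean number of approximal lesions the comparator registers. Under the three stated assumptions, a 1-lesion gain would be fully offset at an approximal share of 32.5%. At a low share the effect would be small.

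Three stronger readings are not supported:

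- **That the trial is underpowered for this reason.** The approximal share, the visible-surface gain and the SD of differences are all missing.
- **That the register figures are known not to be split by surface.** Section 5 is silent on this, and the 1-lesion effect was set by the investigators, not taken from the register.
- **That a surface-limited count would isolate fluorescence.** Scans use white as well as blue light, so it would isolate scanner detection on visible surfaces and no more.

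Nor does the protocol claim that the scanner will replace radiographs. Section 11 speaks only, and conditionally, of possibly reducing the need for them. The point is a worthwhile clarification of the endpoint, not a demonstrated error in the result or the sample size.

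**What to change.** **Section 4.** State that the between-method test of caries detection counts, for both methods, only lesions on surfaces both can examine (occlusal and free smooth surfaces). Always report alongside it the whole-mouth comparison and the number of approximal lesions registered by the comparator. Rest any statement about reducing the need for radiographs on the whole-mouth result.

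**Section 5.** State which surfaces the 3.08 mean covers or, if this is not known, that its value for scanner-visible surfaces is an assumption.

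**Cost.** The text changes are short. Caries must be recorded by tooth surface for both methods, which adds work if it is not already done. The detection claim becomes limited to scanner-visible surfaces, and two results are reported instead of one.

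### The study is sized for initial caries lesions, but Section 4 contains no test of that endpoint and names no primary test

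*Combined protocol and SAP*

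**What the plan says.** **Sizing (Section 5, Sample size calculation).** The plan states that "data regarding initial caries lesions was used for the sample size calculation", on the assumption that the new method will reveal significantly more such lesions than traditional methods. The inputs are register data ("an average of 3.08 initial lesions, with a standard deviation of 1.23 were identified" in 15-year-olds), power ("the desirable power was set on 90" per cent), alpha ("the level of significance on 5" per cent) and a difference of one lesion. The result is 64, raised to 70 for drop-out.

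**Analysis (Section 4).** Three kinds of analysis are planned:
- paired t-tests of clinical caries and erosion scores, baseline against later visits;
- Pearson correlations between clinical and scan scores;
- a paired t-test of lesions per patient, with caries and tooth wear given as the conditions, "that will be detected with the 2 different methods", namely scanning and clinical-radiographic examination.

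The paragraph holding the last two opens by calling the analysis of the scan data exploratory. The section then says: "All statistical analysis will be conducted using a 95% level of confidence". No primary endpoint, primary test, testing order or multiplicity rule appears in the document.

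**Visits (Section 3 and Table 1).** Clinical examination and scanning take place at every examination visit, but "BW radiographs will be repeated only on the final examination". The 3- and 6-month visits are only for participants at moderate or high risk.

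**The concern.** A sample size calculation fixes an endpoint, a comparison and an error rate, and the analysis section should carry the same test. Here it does not. The between-method test is not restricted to initial lesions, includes a second condition (tooth wear) and leaves the visit open.

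The two hypotheses in Section 2a are broad: monitoring will benefit, and changes will be identified earlier. A significant result for either condition at either full visit could therefore be presented as support. The stated 90% power and 5% significance would then describe a test that Section 4 does not contain, while the reported conclusion could rest on another one chosen after the data are seen.

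**Working it through.** **1. Reproduce the plan's figure.** The inputs from Section 5 are a difference of 1 lesion, SD 1.23, alpha 5% and power 90%. Sidedness is not stated. The formula for two independent groups, two-sided, is

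n per group = 2 × (1.960 + 1.282)² × 1.23² / 1² = 2 × 10.51 × 1.513 = 31.8, so 32, and 64 in total.

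This matches the stated 64 exactly. (One-sided with the same difference gives 52. Two-sided with 30% of 3.08 = 0.924 gives 76. One-sided with 0.924 gives 62.) The calculation therefore assumes a single 5% test of a single endpoint, and the formula is for two independent groups.

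**2. Compare the sized test with the written one.**

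| | Section 5 (sizing) | Section 4 (between-method test) |
|---|---|---|
| Lesions | initial caries | caries and tooth wear, any stage |
| Visit | not stated | not stated |
| Alpha | 5%, one calculation | 5% for every analysis |
| Design | two-group formula | paired |
| Status | assumed significant difference | exploratory, or not clear |

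**3. Count the tests that could support the claim.** Only baseline and one year have the full clinical-radiographic comparator. Taking caries and tooth wear as separate tests, that is 2 conditions × 2 visits = 4 tests, or 2 tests if one visit is used. The document states neither count. Both are assumptions drawn from its schedule.

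**4. Chance of at least one false positive in either direction, if independent: 1 − 0.95^k.**
- k = 2: 1 − 0.9025 = 9.75%
- k = 4: 1 − 0.8145 = 18.5%

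Tests on the same patients are probably positively correlated. A simulation of equally correlated tests (400,000 draws) gives, for correlations 0.3 to 0.8:
- k = 2: 9.4% to 7.9%
- k = 4: 17.4% to 11.4%

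**5. Chance of a false result in the scanner's favour.** A two-sided 5% test errs in that direction 2.5% of the time. If independent, 1 − 0.975^k:
- k = 1: 2.5%
- k = 2: 1 − 0.9506 = 4.9%
- k = 4: 1 − 0.9037 = 9.6%

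**6. Does one named paired test need more patients?** Assume SD 1.23 for each method and a between-method correlation of 0. The SD of the differences is 1.23 × √2 = 1.74, and n = 1.74² × 10.51 = 31.8, so 32 patients. With 64 patients the power is 99.5%, and a positive correlation raises it.

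**The case against.** The strongest reply is the word *exploratory*. It opens the paragraph that contains the between-method t-test. If it governs that test, the plan makes no confirmatory claim there, and error inflation is not the main issue. This stands as far as it goes: the scope of the word is unclear, and on that reading the figures in steps 4 and 5 lose most of their force. But the study then has a 90% power calculation for a hypothesis that no confirmatory test addresses. Both readings call for the same correction.

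It can also be said that each single test keeps its nominal 5%. That is true. The point concerns the overall claim when any of several tests may support it. At a single visit the pro-scanner error is 4.9%, close to the nominal figure, though still about twice that of one two-sided test.

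Three stronger readings are tempting, and the documents do not support them:
- **Eight tests.** A reader might count method comparisons at four visits. At 3 and 6 months there are no bitewings and only part of the sample attends, so the clinical-radiographic comparison is not available in full.
- **Fourteen tests.** A reader might add the tests of caries and erosion scores over time. These use clinical scores alone and cannot produce a false finding about the scanner.
- **Dilution.** A reader might infer that including advanced caries or tooth wear shrinks the effect. In a paired difference, lesions seen by both methods cancel, and no discordance data are given. Pooling the conditions into one count would also contradict counting them as separate tests.

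**Conclusion.** The concern holds in limited form. The endpoint that justifies the sample size is not tested in Section 4, and no test is designated as primary. Depending on what *exploratory* covers, either the powered hypothesis has no confirmatory test, or the overall claim is not held at the error of a single test.

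In the second case the supported size is four tests: 18.5% for any false positive if independent (about 17% to 11% at correlations of 0.3 to 0.8), and 9.6% for a false pro-scanner result against 2.5% for one test. At one visit the figures are 9.75% and 4.9%. They assume two-sided tests, two separately tested conditions and no other freedom. The choice between initial and all-stage caries would add some freedom that cannot be quantified from the document.

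This affects how the main result can be interpreted. It does not show that the study is too small.

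**What to change.** In Section 4, name one confirmatory test: the paired per-patient difference in the number of initial caries lesions, scan versus clinical-radiographic examination, at baseline, two-sided 5%. Two definitions must go with it:
- **Initial.** List which of the ICDAS stages already recorded under Section 3 count as initial.
- **Surfaces.** Restrict both methods to the smooth free and occlusal surfaces. The Background says the scanner cannot examine approximal surfaces, so approximal lesions found on bitewings would otherwise count against it by construction.

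Report tooth wear, all-stage caries, later visits, score changes and correlations as estimates with 95% confidence intervals and no confirmatory claim. State that *exploratory* applies to these.

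The cost is a few sentences, and the sample size stays at 64 (70 with drop-out). A Bonferroni correction under the plan's own two-group formula would instead need 76 for two tests or 88 for four. The downside is that the sponsor gives up claiming success on a secondary comparison.

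The named test would agree with the sizing in endpoint and alpha but not in design, because 64 is the total from a two-independent-group formula. Section 5 should say so. Step 6 indicates that 64 is enough for the paired test, provided that the one-lesion difference and the SD of 1.23 carry over to the restricted surfaces.

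### Country and age group are fully aliased and the planned scan-clinical Pearson correlations have no country/age term, so a pooled r may be biased in either direction

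*Combined protocol and SAP*

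**What the plan says.** Section 5 (Research subjects) describes the participants as "adolescents (12-16 years old) and young adults (18-19 years old) in Denmark and in Greece respectively". The two age bands do not overlap. The inclusion criterion in the same section is a single range that is not split by country: "Young people (12-19 years old) without chronic diseases". The sample size paragraph gives one total of 70 and no allocation between Denmark and Greece.

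Section 4 (Statistics) introduces the scan analyses with "Exploratory analysis of the data extracted from the 3D scans will be conducted and compared to the clinical scores" and continues: "Pearson correlation coefficients between the clinical scores and scores obtained from the 3D scans will be calculated". It names no country, site or age term, no stratification and no unit of analysis for the correlation. The other planned link between the two methods is within-patient: "Paired t-test will be conducted to compare the number of lesions per patient".

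Two statements bear on how the scores may behave in the two groups. Section 3 bases the clinical caries record on both sources: "the presence of caries lesions will be registered based on the visual and radiographic assessments". The background in Section 2 says of the scanner that "the areas between the teeth (i.e. the approximal surfaces) cannot be visualized and therefore cannot be examined using the scanner".

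**The concern.** The cohort consists of two populations that differ in country, examining site and age. Section 5 gives its own reason why lesion levels could differ: second molars erupt at about 12-14 years and third molars at 17-18, and teeth carry a higher risk of fissure caries while erupting.

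A Pearson coefficient over both groups mixes two things: how scan and clinical scores vary together among patients within a population, and how the two population means differ. A reader will normally want the first. If the second contributes materially, the coefficient may misstate how closely the scores track each other among Danish adolescents or among Greek young adults. The correlation is one of only two specified comparisons of scan with clinical findings, and Section 4 applies the 95% confidence level to all analyses, so its value and significance are likely to be read.

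**Working it through.** **Inputs.** From the documents: the age and country allocation (Section 5); 70 participants with 10% drop-out, hence 70 × 0.9 = 63 completers; an SD of 1.23 initial lesions among Danish 15-year-olds (Section 5, sample size). Assumed, because the documents are silent: the share p of patients in one group, the within-group correlation r_w, and the between-group gaps in mean score.

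**The plan's own figure.** Section 4 gives no figure for the correlation. The sample size of 64 reproduces from lesion counts alone: 2 × 1.23² × (1.960 + 1.282)² / 1² = 31.8, so 32 per group and 64 in total. The correlation plays no part in it.

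**Formula.** Let both scores have unit SD within each group, and let the group means differ by d_c SD (clinical) and d_s SD (scan). Then

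r_pooled = (r_w + p(1−p)·d_c·d_s) / √[(1 + p(1−p)·d_c²)(1 + p(1−p)·d_s²)].

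**Results for r_w = 0.50.**

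| Gap, clinical / scan (SD) | 50:50 | 25:75 | 10:90 |
|---|---|---|---|
| 0 / 0 | 0.50 | 0.50 | 0.50 |
| 1 / 1 | 0.60 | 0.58 | 0.54 |
| 2 / 2 | 0.75 | 0.71 | 0.63 |
| 1 / 0 | 0.45 | 0.46 | 0.48 |
| 2 / 0 | 0.35 | 0.38 | 0.43 |
| 1 / −0.5 | 0.33 | 0.36 | 0.43 |

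For example, at 50:50, p(1−p) = 0.25. Equal gaps of 1 SD give (0.50 + 0.25)/1.25 = 0.60. A gap in one score only gives 0.50/√1.25 = 0.45.

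**On the lesion scale.** One lesion is 1/1.23 = 0.81 SD. At 50:50, an equal shift of one lesion moves 0.50 to 0.57, and a one-lesion shift in one method only moves it to 0.46. The SD is described as lying across municipalities, so it serves only as a rough scale.

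**Sampling error for comparison.** With n = 64 and r = 0.50, the Fisher z interval is tanh(0.549 ± 1.96/√61) = 0.29 to 0.66.

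**Extreme case.** With r_w = 0 and equal gaps d at 50:50, r_pooled = 0.25d²/(1 + 0.25d²). The two-sided 5% critical value for n = 63 is 2.00/√(2.00² + 61) = 0.248, which is reached at d of about 1.15. With 10% of patients in the smaller group, the same gap gives 0.09 × 1.15²/(1 + 0.09 × 1.15²) = 0.11, well short of 0.248. These thresholds also assume one pair of scores per patient, which Section 4 does not say.

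**The case against.** A reader might infer that pooling will inflate r, so that any gap between Danish and Greek patients counts as agreement between the methods. The documents do not support that.

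- **Direction.** Inflation needs gaps in the same direction and of similar size in both scores. The documents give a reason why they may be unequal: the clinical record draws on bitewing radiographs, while the scanner cannot see approximal surfaces. Section 5 adds that in older patients "such initial lesions are located on the surfaces between the teeth, which are not visible to the intraoral scanner", although that sentence concerns people beyond the study's age range and is only suggestive.
- **Existence of a gap.** No lesion level is given for Greek 18-19-year-olds. The only figures are for Danish 15-year-olds.
- **Pooling.** It is inferred from silence, one total N and one inclusion range. Section 4 never says that the groups are combined.
- **Role of the correlation.** The scan analysis is called exploratory, and the plan does not present Pearson r as a measure of agreement. A main effect of country cancels in the paired t-test.
- **Size.** An equal one-lesion shift moves r by 0.07, well inside the sampling interval. The case of a significant r from no within-group association needs the scanner to reproduce a gap of more than 1 SD between groups yet track nothing within them.
- **Estimand.** If both methods find more lesions in one group, that is shared signal over a wider range of disease, and a pooled r may legitimately describe it.

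All of this stands and limits the point. It does not remove it: bias in either direction makes a lone pooled r hard to interpret, sampling error does not cancel a systematic shift, and the plan does not say which association it intends to estimate.

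**Conclusion.** The point holds in a limited form. Country and age group are completely aliased, and Section 4 plans no analysis by either. If the groups are pooled, r may differ from the within-population association: up if both scores shift together by similar amounts, down if one shifts alone or they shift in opposite directions, and unchanged if neither shifts. With within-group r = 0.50 and gaps of 1 SD, the plausible movement at an equal split is to 0.60 or to 0.45; it is smaller with an unequal split. These sizes rest on assumed splits, gaps and within-group correlations. The within-patient comparison of lesion counts is not biased by a main effect of country, although a scanner gain that differed between the groups could not be attributed to country rather than age. Severity is low, because the correlation is exploratory and the study was not sized on it.

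**What to change.** Add to Section 4:

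1. State whether r is pooled, and on what unit (patient, tooth or surface).
2. Report the scan-clinical correlation within each country/age group, with a combined estimate beside any pooled r. The combined estimate can be a Fisher z average or a partial correlation adjusted for country.
3. Show the per-patient difference in lesion count between methods, with its 95% CI, by group as descriptive output.

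This takes a sentence or two and a few more lines of output; country is known for every participant, so no new data are needed. The cost is wider intervals for each group. At r = 0.50 with 32 patients per group (an assumed equal split of 64), each interval is tanh(0.549 ± 1.96/√29) = 0.18 to 0.72. The combined Fisher z estimate loses almost nothing: tanh(0.549 ± 1.96/√58) = 0.28 to 0.67, against 0.29 to 0.66 for a single sample of 64.

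The change removes the between-group component from r. It does not separate country from age, which this design cannot do, and the report should say so.
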